## B. Intervention

Subjects (parents of neonates) will receive an ointment and cloths with standardized instructions for use. The instructions will be the same for all subjects. Approximately 1 cm ribbon of ointment will be self-administered by inserting a new cotton-tipped applicator into each anterior nares. A new cotton-tipped applicator will be used for each nares followed by gentle massaging of the nares to ensure distribution of the ointment. This procedure will be performed twice daily for five days. Verbal and printed instructions will be provided to parents. Study staff will demonstrate application of mupirocin ointment to the anterior nares. Parents will self-administer all doses of the intervention. Subjects will also be given pre-packaged cloths for daily skin cleaning. Each package contains 6 cloths. Each cloth will be used to wipe a designated body area (arms, legs, chest and neck, back and perineum) once a day for 5 days. Study staff will demonstrate how to apply CHG to the skin and instruct parents to not rinse after using the cloths. Participants will be instructed to perform the baths on the same 5 days they apply the intranasal ointment.

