## **9. Statistical Analysis Plan**

### **A. Sample size and power estimates:**

The primary outcome will be time to concordant *S. aureus*-colonization. Time to concordant *S. aureus* colonization will be expressed using an indicator variable for concordant colonization and time to concordant colonization. The a priori assumed

control group concordant colonization rate is 10% and power calculations are based on the unadjusted Cox proportional hazards model where the primary covariate is the treatment group indicator. In time to event analyses, power is driven by the number of events; i.e. number of concordant colonizations. Given our assumed control group concordant colonization rate of 10%, 38 events are required to detect a 60 percent reduction in the hazard of concordant colonization (Hazard Ratio: HR 0.4) in the intervention group with 80% power and Type I error rate of 5%. The 38 events includes a roughly 2% inflation for pre-planned interim analyses (see Section 9.B). Given that we expect 5% of the parent-neonate pairs will be non-singleton births, we increased the number of required events to 40 to account for the possible clustering of concordant colonization among non-singleton neonates. Some neonates may test positive at baseline for *S. aureus* after randomization and will not be eligible for the analysis of the primary outcome. Similarly, if one neonate from a multiple gestation birth is positive for *S. aureus* at baseline and another neonate is not, then the negative infant will be eligible. Eligible parent-neonate pairs will be assigned to either treatment or control as a unit until 40 events are confirmed. Prior to the start of the study, given our *a priori* assumption of a 10% concordant colonization rate in the control group and a HR of 0.40, we anticipated recruiting 400 parent-neonate pairs to achieve the required 40 concordant colonizations. With 400 parent-neonate pairs, we have roughly 80% power to detect an absolute risk difference of at least 7% for the secondary analysis of the indicator of concordant colonization within 90 days after randomization.

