### **C. Statistical analysis plan**

Final analysis methods and changes in the analyses from those described in the protocol will be documented in the Statistical Analysis Plan prior to locking the database and unmasking the assignment. A CONSORT flow diagram will be created. In addition, descriptive statistics will be calculated to describe the feasibility of the study including number of parent-neonate units approached by a study team member, proportion of parents that consent, proportion of parents colonized among consented, proportion of parents colonized who subsequently do not complete the treatment, and the distribution of adherence, as defined below, to the randomized treatment.

Analyses will be conducted according to the modified intention to treat (mITT) principal. The same day parents are randomized, the neonate will undergo baseline testing to determine baseline *S. aureus* colonization status. Neonates who test positive for *S. aureus* colonization at the time of randomization do not satisfy the inclusion criteria and will not be included in the analysis; hence defining the modified intention to treat analysis. Exploratory analyses of baseline characteristics for the treatment groups will be evaluated by Student t test for continuous data and Pearson's  $\chi^2$  test or Fisher Exact test for categorical data. No missing data should occur for baseline parent and neonate variables. No missing primary or secondary outcomes are expected. However, it is possible that neonates have no subsequent cultures between the baseline culture and NICU discharge, e.g. a neonate enters the study on Friday and is discharged on Sunday prior to their scheduled surveillance culture (Friday in this example) or discharge culture. Based on our definition of observation time (see Sections 5.A and 5.B), such neonates

will contribute no observation time for the analysis of the primary and secondary outcomes. A sensitivity analyses will be conducted where the observation time for these neonates will be defined as the time from randomization to NICU discharge. All tests will be 2-sided with a type-1 error rate set at 0.05. Data will be managed and analyzed using Stata, version 13.0 (Stata Corp., College Station, TX) and R: A language and environment for statistical computing (R Foundation for Statistical Computing, Vienna, Austria, 2014).

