We will conduct a per protocol (PP) analysis. Compliance to treatment will be defined first for the individual parent and then for the family or parent/neonate dyad (Table 4). Individual parents will be classified as: confirmed compliant where the parent returns a treatment kit with ointment tubes with a broken seal; reported compliant where the parent gave responses to questions about feasibility and potential adverse effects (see Section 4.B compliance monitoring); and non-compliant where a) kits were returned unused, b) the parent reported non-use, or c) parent was lost to follow up without reporting use. We will define *compliance to treatment* for the individual parent as confirmed compliant, with a sensitivity analysis including reported compliant in the definition of *compliance to treatment*. Family compliance will be defined as both parents satisfying the *compliance to treatment* definition, with a sensitivity analysis where we include partially compliant families, i.e. if the parent identified to be colonized with *S. aureus* is compliant based on the individual parent definition and the non-colonized parent is non-compliant. Baseline characteristics of the parents, including age, race, education level, and recent antibiotic use, will be compared across the individual parent compliance definitions, overall and separately by treatment group. Baseline characteristics of the ITT and PP neonates will be compared, overall and separately for each treatment group. The analysis of the primary and secondary outcomes described above will be repeated among the subset of parent/neonate dyads who are observed to be compliant. Note, that we will assume that all placebo group patients are compliant. We will conduct the PP subset analysis using this assumption and then separately incorporating the compliance definitions above to the placebo group as well. Conditioning on compliance, a post-randomization variable, may introduce bias into any treatment comparisons. Therefore, we will also implement a causal inference approach using available baseline parent and neonate variables within an inverse probability weighted approach to estimate the treatment effect for the primary and secondary outcomes, where the treatment effect compares what would have happened if all patients receiving the treatment were compliant vs. if all patients receiving the placebo were compliant.

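### The first-listed per-protocol analysis filters only the active arm for compliance, so it can be biased in either direction even if treatment does nothing, and no per-protocol version is named as the main one

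*Combined protocol and SAP*

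**What the plan says.** The per-protocol paragraph of section 9.C, with Table 4, classifies each parent and then each family. A parent is non-compliant if the kit came back unused, if the parent reported not using it, or if the parent was lost to follow-up without reporting use. The main definition of a compliant family requires both parents to be confirmed compliant, which means a returned kit with a broken ointment seal. Self-reported use counts only in a sensitivity analysis.

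The primary and secondary analyses are then repeated in families observed to be compliant. For the placebo arm the plan departs from observation: "we will assume that all placebo group patients are compliant". The subset analysis is run on that assumption first, "then separately incorporating the compliance definitions above to the placebo group as well".

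The same paragraph warns in general terms that conditioning on a post-randomization variable may bias comparisons. It adds an inverse probability weighted analysis that contrasts full compliance on treatment with full compliance on placebo. It gives no reason for the placebo assumption and does not say which version is the main per-protocol analysis.

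Section 4.B says of the study products: "The instructions will be the same for all subjects". Its compliance-monitoring text applies the daily contact and the request to return the tube to every participant, whichever ointment was supplied. The allocation section (4.C.6) masks participants, investigators and treating clinicians.

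**The concern.** Placebo compliance is observable by the same means as active compliance, so nothing in the design requires it to be assumed. Under the assumption, the active arm is reduced to a selected group of families while the placebo arm stays whole. Families who comply may differ from those who do not in visiting, holding or hygiene. Any such difference that affects acquisition of *S. aureus* then becomes part of the estimated treatment effect.

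It might be argued that compliance with an inert product does not matter. That argument concerns what the product does. The difficulty here is which families are selected, and it arises even if neither product has any effect.

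At stake is the reading of one supporting analysis. The one-arm version is listed first, covers both primary and secondary outcomes, and could be reported as the per-protocol result because no other version is given precedence.

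**Working it through.** **The plan's own figures.** The plan gives no figure for the per-protocol analysis. Its event target sets the scale of precision: "38 events are required to detect a 60 percent reduction in the hazard of concordant colonization". With two-sided 5% error, 80% power and 1:1 allocation (the ratio is assumed), Schoenfeld's formula gives 4 × (1.960 + 0.842)² / (ln 0.4)² = 37.39, or 38 after rounding up. With the 2% interim inflation it is 37.39 × 1.02 = 38.14. The stated figure is reproduced and is not in dispute.

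**Inputs.** Let p be the proportion of compliant families and r the acquisition hazard of compliers' neonates divided by that of non-compliers' neonates. The documents give neither, so both are assumptions. To illustrate how p could fall, if 84% of parents met the confirmed definition independently, 0.84² = 0.71 of two-parent families would qualify.

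**Null hazard ratio of the one-arm filter.** Suppose treatment has no effect and non-compliers have hazard h.

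- The filtered active arm has hazard r·h.
- The unfiltered placebo arm has average hazard p·r·h + (1 − p)·h. The simple average is adequate because events are uncommon (10% assumed in controls).
- Apparent HR = r / (p·r + 1 − p).

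For example, p = 0.7 and r = 0.6 give 0.6 / (0.42 + 0.30) = 0.83.

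| p | r = 0.6 | r = 0.8 | r = 1 | r = 1.25 | r = 1.5 |
|---|---|---|---|---|---|
| 0.6 | 0.79 | 0.91 | 1.00 | 1.09 | 1.15 |
| 0.7 | 0.83 | 0.93 | 1.00 | 1.06 | 1.11 |
| 0.8 | 0.88 | 0.95 | 1.00 | 1.04 | 1.07 |
| 0.9 | 0.94 | 0.98 | 1.00 | 1.02 | 1.03 |

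With the same filter in both arms, each arm has hazard r·h and the ratio is 1.00. This assumes that compliance has the same causes in both arms.

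**Chance of a misleading result.** The simulation used 200 families per arm, 10% true risk in each arm, a two-proportion test as a stand-in for the Cox test, and 40,000 runs per scenario. The nominal rate is 2.5% in each direction.

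- Non-compliers at 1.5 times the risk of compliers (r about 0.67): a false benefit appears in 6.4%, 5.6%, 4.4% and 3.5% of trials at p = 0.6, 0.7, 0.8 and 0.9. At p = 0.7 the apparent HR is 0.86.
- Non-compliers at half the risk (r = 2, beyond the table): false harm appears in 10.9%, 8.0%, 5.5% and 3.7%. At p = 0.7 the apparent HR is 1.19.
- Same filter in both arms: a false benefit appears in 2.3% to 2.6% in every scenario.

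**Bias against precision.** With 40 events, the standard error of the log hazard ratio is about 2/√40 = 0.32, so a 95% interval runs from about 0.54 to 1.86 times the estimate. At p = 0.7 and r = 0.6 the bias is ln 0.83 = −0.18, or 0.18 / 0.32 = 0.6 standard errors.

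**The case against.** The strongest reply is that the plan already holds most of the remedy. The both-arm version is pre-specified directly after the assumption, a weighted analysis follows, and the bias from conditioning on compliance is acknowledged. Section 9.C also compares baseline characteristics across parent compliance categories, and between the intention-to-treat and per-protocol neonates, by treatment group. Seeing the one-arm and both-arm results together could even show a reader how much selection there was. All of this stands, and it limits what remains to one avoidable contrast and the missing order of precedence.

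Second, no trial decision rests on this analysis. The primary analysis is modified intention to treat, and the boundaries in section 9.B apply to that outcome and model. This also stands.

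Third, a reader might infer that the one-arm filter will favour the active treatment. The documents do not support that. They give no data on how compliance relates to risk. The Synopsis and section 2.B say that skin-to-skin contact may promote transmission, so families who comply more and also hold their infants more could carry higher risk, which would produce apparent harm.

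Fourth, the size depends on compliance that nobody yet knows. At 90% compliance the apparent HR stays between 0.94 and 1.03 over the range shown, and throughout the table the bias is smaller than the sampling error of about 40 events. This is fair, but a fixed bias that is easily avoided need not be accepted because the interval is wide.

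**Conclusion.** The point holds and is minor. The first-listed per-protocol analysis compares a selected active arm with an unselected placebo arm, without a stated reason and although compliance is measured the same way in both. Over the assumed ranges the null hazard ratio lies between about 0.79 and 1.15. At 70% compliance it is 0.83 to 0.93 for r of 0.6 to 0.8, and 1.11 for r of 1.5. There is no bias if compliance and risk are unrelated.

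Two stronger readings should be resisted. One is that the plan offers no symmetric per-protocol analysis: it does, but does not give it precedence. The other is that the trial's main conclusion or its stopping rules are at risk: neither uses the compliance subset.

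**What to change.** Delete the assumption that all placebo families comply. Name the both-arm version already planned, using the Table 4 definitions in each arm, as the per-protocol subset analysis, and report it beside the inverse probability weighted analysis. If the one-arm version is kept, label it supplementary and a non-randomised comparison.

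This is a change of wording, and section 9.C already provides for analysis changes to be documented before database lock and unmasking. The cost is a smaller placebo per-protocol set and a slightly wider interval. The change removes the asymmetry but does not make the subset a randomised comparison. If reasons for non-compliance differ by arm, for instance through reactions to the active products, the both-arm version can still be biased. The plan's existing caution should therefore stay.

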**Table 4: Definition of individual parent and family compliance to treatment**

Individual parent compliance assessment		
Category	Sub-category	Definition
Compliant	Confirmed compliant	seal broken on nasal ointment
	Reported compliant	participants reported use
Non-compliant	Confirmed non-compliant	kits were returned unused
	Reported non-compliant	parent reported non-use
	Presumed non-compliant	parent was lost to follow up without reporting use
Family- level compliance assessment		
Category	Individual 1 compliance	Individual 2 compliance
Compliant	Compliant	Compliant
Partially compliant +	Compliant (SA colonized)	Non-compliant (not SA colonized)
Non-compliant	Compliant (not SA colonized)	Non-compliant (SA colonized)
Non-compliant	Non-compliant	Non-compliant

+partially compliant if *S. aureus* colonized parent is compliant, even if the non-colonized parent was non-compliant

Lastly, within each treatment group, we will use standard survival analysis methods (e.g. Kaplan-Meier survival function curve) to explore the loss of and potential reacquisition of *S. aureus* among the parents, separately for each treatment group. Cox proportional hazards models will be used to describe the association between loss of and reacquisition of *S. aureus* with baseline parent characteristics and treatment.

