### **D. Secondary Hypotheses**

Many neonates acquire *S. aureus* in the NICU from their parents

Treating *S. aureus* colonized parents of neonates requiring NICU care with intranasal mupirocin and topical chlorhexidine bathing will reduce neonatal *S. aureus* infections.

Treating *S. aureus* colonized parents of neonates requiring NICU care with intranasal mupirocin and topical chlorhexidine bathing will reduce parental *S. aureus* colonization.

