## **5. Screening**

The PI and/or a member of the research team will provide information regarding the study, answer any questions and obtain informed consent. The PI will be available in person or via telephone to answer any questions when a member of the research team is present for the consent. As part of the informed consent document, the subject will receive information on how to contact a study team member to discuss culture results or any noted treatments that may be related to *S. aureus*. Once consented, a member of the research team will assign a screening number (SN) to the subject. If the cultures are positive, the family unit will be enrolled and assigned a study identification number (SIN). This will be the primary mode of identification throughout the study. The SIN will identify the parent and the neonate (or neonates in the case of multiple gestations). The SIN will also identify both parents (if both consent to participate as both will be assigned to the treatment group). The SIN and/or SN will appear on the consent form, the data collection form, as well as all *S. aureus* cultures. If the cultures test negative, the family unit will not be randomized to treatment. However, parent participation in the study will not end. They will be asked to continue their participation in the study by completing a follow-up questionnaire approximately four weeks after their initial screening visit.

During the screening visit, a member of the research team will perform the necessary swabs to be sent for culture. The parent(s) who consent to undergo testing will be screened by obtaining a swab from the following anatomical sites: bilateral anterior nares, the throat, the groin/perineum, and the peri-anal area. A standardized check-list for obtaining and processing swabs will be used. For neonates transferred from an outside hospital or from home that did not have surveillance cultures obtained on admission, screening cultures will be performed by obtaining a swab from the following anatomical sites: bilateral anterior nares, umbilicus, groin, and peri-anal area.

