All swabs will receive a study number pre-printed on a label. The SN will not identify the patient's name, medical record number or other identifying information. The SN will be recorded on the informed consent documents and the surveillance swabs. Before sending the swabs, a member of the research team will take a brief "time-out" to reassess that all paperwork is completed, that swabs are appropriately labeled with SN, and that all consent forms and swabs contain the same SN.

Laboratory methods for determining whether a patient has *S. aureus* colonization are described below in Section 7.B. *S. aureus* colonization will be defined as a culture from any anatomic site that grows *S. aureus*.

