## 6. Allocation

**Randomization and masking:** This study has taken into consideration the guidelines for reporting of clinical trials as recommended by the CONSORT report to inform the study design. After recruitment and informed consent, parents will undergo pre-randomization screening. If both parents screen negative for *S. aureus* colonization, the neonate will be ineligible for the randomization and parents will be informed that they are not colonized at that time with *S. aureus*. If either parent screens positive for *S. aureus*, then both parents as a pair will be eligible for randomization to one of the two possible masked treatment arms. The neonate-parent "pair" will be the unit of randomization and each parent will be allocated to the same group if both consent. Because couples can re-expose each other after treatment (especially in households) we have chosen to treat both parents even if only one parent is colonized with *S. aureus*. To prevent potential feelings of guilt or one parent blaming another if only one parent is colonized, the parents will be told that one or both is colonized with *S. aureus* and they are eligible for randomization. Discordant parents will not be informed which is colonized and which is not colonized as we will treat both regardless.

Arm 1 will include assignment to masked intranasal mupirocin plus chlorhexidine gluconate cloths for topical antisepsis. Arm 2 will include assignment to masked placebo ointment and placebo cloths for skin antisepsis. Stratified permuted-block randomization will be performed using R statistical software to achieve balanced allocation of subjects within study site (Johns Hopkins Hospital vs. Bayview) and within strata of birth weight

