## D. Follow-up

**Parent Evaluation Time Points:** After randomization, the study team will provide the study drugs, study drug application instruction sheets and informational material. All participants will begin the 5-day treatment course at that time. During the 5-day treatment period, a study team member will contact the study participant daily at the bedside, on the phone, by email or by text message to assess compliance with treatment and to answer any questions. When available, parent(s) will be re-tested for colonization at 2-week intervals from randomization for the first 8 weeks and then every four weeks until discharge. Follow up swabs may be taken within a week of scheduled time points, based on participant availability. Anatomic sites to be tested and frequency of testing are detailed in Table 1. Peri-anal swabs will only be collected at enrollment and final screening. The final visit and testing will be performed at the time of a neonate's discharge from the NICU or at the time the child is identified to have acquired *S. aureus*.

**Neonate Evaluation Time Points:** After informed consent and randomization of parents, the neonate will undergo baseline testing to determine baseline *S. aureus* colonization status. This testing will occur on study day 1, the same day that parents begin treatment. Screening cultures will be performed by obtaining a swab from the following anatomical sites: anterior nares, the umbilicus, groin, and peri-anal area. If the nares site is not available to swab, the throat will be swabbed instead. Those neonates who test positive for *S. aureus* colonization at time of randomization will not be included in the primary analysis. After baseline testing, repeat testing will be performed every 7 days. Study samples will be saved and processed in the lab. The final visit and testing will be performed at the time of a neonate's discharge from the NICU.

Table 1

Frequency of Parent Swab Collection			
Site	Screening	Weeks 2, 4, 6, 8, 12, 16, 20, 24, 28,....	Time Neonate Acquires S. aureus
Nares	X	X	X
Throat	X	X	X
Groin	X	X	X
Peri-anal	X		X

Table 2

Frequency of Neonate Swab Collection			
Site	Parent Randomization	Weeks 1, 2, 3, 4,....	NICU Discharge
Nares	X	X	X
Umbilicus	X*	X*	X*
Groin	X	X	X
Peri-anal	X	X	X

\*Umbilicus will only be tested if the neonate has attached umbilical cord.

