**3. Eradication of *S. aureus* colonization in parents following treatment**

**Outcome ascertainment** – Parents will be monitored as described above in section 4.D to monitor *S. aureus* colonization over time. Parents will be tested at baseline, and then every two weeks for the first two months, if available, while neonate remains in the NICU, monthly starting on third month their neonate remains in the NICU, at the time the infant acquires *S. aureus* colonization in the NICU, and at time of discharge from the NICU for a neonate that did not acquire *S. aureus* colonization in the NICU.

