#### **4. Natural history of *S. aureus* colonization in parents receiving placebo**

**Outcome ascertainment** – same as above for parents receiving placebo

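### If the any-site colonization rule is carried to three-site interim visits, remaining peri-anal carriage in parents can be scored as loss and later as reacquisition; the parent Cox models also name no family-level variance.

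*Combined protocol and SAP*

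**What the plan says.** Screening (Section 4.C.5) swabs each parent at four sites: "bilateral anterior nares, the throat, the groin/perineum, and the peri-anal area". The same section gives the document's only colonization rule: *S. aureus* "colonization will be defined as a culture from any anatomic site that grows" the organism.

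Follow-up (Section 4.D) retests parents, when available, every two weeks to week 8 and every four weeks after that. It adds: "Peri-anal swabs will only be collected at enrollment and final screening". Table 1 agrees, with the peri-anal row blank at weeks 2, 4, 6, 8, 12 and onward. The final visit falls at the neonate's NICU discharge or when the neonate acquires *S. aureus*.

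Three stated aims depend on these swabs:
- the secondary hypothesis in Section 3.D that intranasal mupirocin and "topical chlorhexidine bathing will reduce parental" *S. aureus* colonization;
- secondary outcome 3, eradication of "colonization in parents following treatment";
- secondary outcome 4, the natural history of "colonization in parents receiving placebo".

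Section 9.C, after Table 4, gives the analysis: "we will use standard survival analysis methods (e.g. Kaplan-Meier survival function curve) to explore the loss of and potential reacquisition of" *S. aureus* among parents, by arm. Cox models then relate loss and reacquisition to baseline parent characteristics and treatment. Loss and reacquisition are not defined, and no variance method is named.

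On assignment, Section 4.C.6 says "each parent will be allocated to the same group if both consent", and gives re-exposure between partners as the reason for treating both. The bootstrap that resamples parent/neonate dyads is introduced in 9.C for multiple-gestation neonates. It is extended there to the neonatal secondary outcomes, the subgroup tests and the covariate-adjusted estimates, but not to the parent models.

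**The concern.** A time-to-loss analysis needs the same definition of colonized at every visit. Here the set of sites shrinks after screening and expands again at the final visit. Under the any-site rule, a parent who still carries the organism only in the peri-anal area yields no positive culture at week 2 and counts as a loss. When the fourth site is swabbed again at the final visit, the same unbroken carriage counts as a reacquisition. Both events would come from the swab schedule.

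This covers parents who were peri-anal-only at screening. It also covers parents who cleared their other sites and kept the peri-anal one. At stake are the Kaplan-Meier curves in both arms, including the description of natural history under placebo, and the hazard ratios for treatment on loss and reacquisition.

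The second gap concerns precision. Treatment is constant within a family, and the protocol itself gives a reason for partners' outcomes to be linked. A Cox model that treats parents as independent then gives too small a standard error for treatment if that link is positive.

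**Working it through.** The documents state no sample size, event count or power for the parent analysis, so there is no planned figure to reproduce. They also do not give the peri-anal-only share, the true clearance rates, the number of two-parent families or the within-couple correlation. These are assumed below and shown as ranges.

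**False loss within an arm.** Let c be true clearance at an interim visit and q the share of still-colonized parents whose carriage is then only peri-anal. Observed loss = c + (1 − c)q, and the false share of counted losses = (1 − c)q / observed loss.
- c = 30%, q = 5, 10, 20%: observed 33.5, 37.0, 44.0%; false share 10.4, 18.9, 31.8%.
- c = 20%, same q: observed 24, 28, 36%; false share 16.7, 28.6, 44.4%.
- c = 60%, same q: observed 62, 64, 68%; false share 3.2, 6.3, 11.8%.

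Observed loss is never below c, so within an arm the error runs one way.

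**Treatment contrast.** Take true loss of 60% treated and 30% placebo, a difference of 30 points.

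| q treated | q placebo | Observed treated | Observed placebo | Difference |
|---|---|---|---|---|
| 5% | 5% | 62.0% | 33.5% | 28.5 |
| 10% | 10% | 64.0% | 37.0% | 27.0 |
| 20% | 20% | 68.0% | 44.0% | 24.0 |
| 20% | 5% | 68.0% | 33.5% | 34.5 |
| 5% | 20% | 62.0% | 44.0% | 18.0 |

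The contrast is inflated when q(treated) × (1 − c treated) exceeds q(placebo) × (1 − c placebo). Here that means a ratio of q above 0.70/0.40 = 1.75. With true losses of 70% and 20% it means a ratio above 0.80/0.30 = 2.67.

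**False reacquisition.** Let r be the share of parents with persistent peri-anal-only carriage. Suppose half of the others clear by week 2 and recolonize at 10% per two-week interval, with a four-site final visit at week 6. True reacquisition among those cleared is 1 − 0.9² = 19%. Observed reacquisition among counted losses = [0.19 × 0.5(1 − r) + r] / [0.5(1 − r) + r]. For r = 5, 10, 20% this is about 27, 34 and 46%.

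**Family clustering.** Only parents positive at screening can lose colonization, so clustering arises in families where both partners are colonized. Let s be the share of such families among eligible ones, and ρ the within-family correlation of outcomes. The mean-square-to-mean family size is (1 + 3s)/(1 + s), so the design effect DE = 1 + ρ × 2s/(1 + s). The ordinary standard error is too small by 1 − 1/√DE.

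For s, use the 30% prevalence in healthy adults quoted in Section 6.D:
- Half of families two-parent, partners independent at baseline: s = (0.5 × 0.09)/(0.5 × 0.51 + 0.5 × 0.30) = 0.045/0.405 = 0.111.
- All families two-parent, independent: s = 0.09/0.51 = 0.176.
- All two-parent, baseline correlation 0.3: both colonized = 0.09 + 0.3 × 0.21 = 0.153; s = 0.153/(0.60 − 0.153) = 0.342.

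Results:
- s = 0.111: ρ = 0.1, 0.3, 0.5 gives DE 1.020, 1.060, 1.100; standard error 1.0, 2.9, 4.7% too small.
- s = 0.176: DE 1.030, 1.090, 1.150; 1.5, 4.2, 6.7% too small.
- s = 0.342: DE 1.051, 1.153, 1.255; 2.5, 6.9, 10.7% too small.

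A higher prevalence would raise s. The extreme, with both partners analysed in every family and ρ = 0.5, is DE 1.50, or a standard error 1 − 1/1.225 = 18% too small.

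**The case against.** The strongest reply is that the any-site rule sits in the Screening section and nothing applies it to interim visits or says that an unswabbed site counts as negative. Section 9.C also leaves final methods to be documented before database lock and unmasking. On this view an exploratory endpoint is simply undefined. That stands in part: a reader might infer that the plan prescribes the faulty scoring, and it does not. But it offers no other rule, and an analyst following the text would use this one.

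A reader might also infer that false losses must fall more heavily on placebo and so dilute the treatment effect. The documents do not support that. It needs an equal peri-anal-only share among still-colonized parents in both arms. The regimen in Section 4.B is directed at named sites, so treatment could change where remaining carriage sits, and the sign could reverse.

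On exposure, parents are retested only when available, and eligibility requires only an anticipated stay of more than five days. A parent whose first follow-up is the final visit has four sites at both ends and is unaffected. On clustering, low correlation with few couples both colonized leaves only about a 1% error. All of this limits the weight of the point, but neither gap is closed by it.

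**Conclusion.** The concern holds in conditional form and is minor. If the any-site rule is used at interim visits, clearance is overstated within each arm, including under placebo, and some reacquisitions at the final visit can be false. The effect on the treatment contrast has no fixed direction: dilution under equal peri-anal-only shares, possible inflation if that share is sufficiently higher under active treatment. Its size cannot be set from the documents; the figures above rest on assumed clearance, peri-anal-only shares and visit attendance.

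Eradication judged from screening to final visit on four sites is not affected by the mismatch, so it would be wrong to infer that secondary outcome 3 is lost. Only interim timing is exposed.

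The missing family-level variance is a separate, modest fault. If partners' outcomes are positively correlated, the treatment standard error is about 1% to 11% too small over correlations of 0.1 to 0.5, given 30% prevalence and the family mixes assumed. The primary outcome, its event target and the interim boundaries are untouched.

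**What to change.** In the SAP, before database lock:

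1. Define interim loss and reacquisition on nares, throat and groin at every visit, screening and final visit included, among parents positive at one of those three sites at screening. Label the result as loss from those sites. Report four-site eradication as screening versus final visit. Keep an any-site version as a sensitivity analysis.
2. Use standard errors clustered on family, or a bootstrap that resamples families, for the parent Cox models, and resample families for the Kaplan-Meier intervals.

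No new swabs are needed. The planned subgroup analysis by parents' colonized site concerns the neonatal primary outcome and does not solve this problem, but it already relies on site-level parent results.

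The cost is that parents positive only peri-anally at screening leave the main interim analysis. If they are an assumed 5% to 20% of colonized parents, standard errors rise by 1/√(1 − x) − 1, about 2.6% to 11.8%, taking precision as proportional to the number of parents. With positive within-family correlation, clustered intervals will be slightly wider.
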